4.5.2 SAFETY ENDPOINT

The safety endpoint of this study consists of the evaluation of adverse events and/or device deficiencies reported with the use of the CathVision ECGenius® System during the procedure until discharge.

The detailed methods to analyze the primary and safety endpoints will be included in the Statistical Analysis Plan (SAP).

4.6 STUDY PROCEDURES

The following is a detailed list of study visits and the required procedures/tests per visit. Specific procedures/tests are described in Section 5.

4.6.1 INFORMED CONSENT

Pre-screening, i.e., medical record review without obtaining informed consent, is allowed.

Prior to enrollment of any subjects into the study, written approval of the protocol and informed consent must be obtained from the Ethics Committee (EC).

Informed consent will be obtained as outlined in the EU Regulation 2017/745, ISO14155:2020 and local legislation.

A research study member at the EC approved study site will speak with the study candidate about the purpose of the study and investigational research. Explanation of the study background, study

procedures, visits, assessments, risks, and benefits will be reviewed in detail with the potential subject. Subjects must be informed about their right to withdraw from the clinical investigation at any time and for any reason without sanction, penalty or loss of benefits to which the subject is otherwise entitled. Withdrawal from the clinical investigation will not jeopardize their future medical care or relationship with the investigator.

The potentially enrolled subject will be given the time they need to read through the study information and informed consent document and ask as many questions as necessary to make them comfortable with the study and the requirements. The subject shall be provided with the Informed Consent form written in a language that is understandable to the subject and has been approved by the EC. After informed consent is obtained, study assessments may begin.

After informed consent is obtained, the study eligibility criteria are verified. All patients who signed a consent form are considered study subjects. A patient is considered enrolled after the patient has signed the informed consent form and after the inclusion/exclusion criteria have been met.

The original informed consent form will be retained with the subject records. A copy of the informed consent will be provided to the subject or legal representative.

Failure to obtain informed consent from a subject prior to clinical investigation enrolment should be reported to Sponsor within 5 working days and to the reviewing EC according to the EC's reporting requirements.

If, during the clinical investigation, new information becomes available that can significantly affect a subject's future health and medical care, the Principal Investigator or authorized designee (if applicable) will provide this information to the subject. If relevant, the subject will be asked to confirm their continuing informed consent in writing.

4.6.2 SUBJECT IDENTIFICATION

To maintain confidentiality, the subject's name will not be recorded on any study document other than the informed consent form. Each enrolled subject will be assigned a study specific Subject Identification Number (SID) to be assigned in consecutive order in the following format: CVAR00002-OLVYYY. CVAR00002 is the study number, OLV is the site identifier, and YYY is the 3-digit sequential subject ID number starting with 001. For example, the first subject at the site will be assigned CVAR00002-OLV001. Subject ID numbers will not be re-used (e.g., if the subject is determined to be a screen failure).

4.7 STUDY VISITS

This section contains a detailed list of visits, from screening to discharge, and the required procedures/tests for each of them.

4.7.1 SCHEDULE OF ASSESSMENTS

	Screening	Index Procedure	Discharge
Visit Number	1	2	3
Informed Consent	✓		
Demographics	✓		
Cardiac History	✓		
Cardiac Anti-Arrhythmia Medications	✓		
Inclusion/Exclusion	✓		
12 lead EKG	✓		
EP procedure		✓	
Adverse Events		✓	✓
Device Deficiencies		✓	✓
Protocol Deviations	✓	✓	✓

4.7.2 VISIT 1: DAY -15 ± 15 (SCREENING VISIT)

Screening will be completed within 30 days of the index ablation procedure.

Test results from routinely performed standard assessments may be used to determine eligibility. Preliminary screening will consist of a review of relevant cardiac history, including duration and frequency of arrhythmia(s), their subsequent treatments (e.g., medications, previous ablation), and associated symptoms.

Eligibility will be assessed sequentially, starting with the least invasive and least expensive tests as follows. Results from each test or screening activity should be reviewed prior to proceeding to the next step.

- Demographics
- Baseline cardiac history
- Arrhythmia history (Type of arrhythmia, TTM, EKG, Holter, etc.)
- Baseline cardiac anti-arrhythmia medications
- 12-lead EKG

4.7.2.1 SCREEN FAILURES

Subjects not meeting all study entry criteria will be designated as screen failures. End of study procedures will not be performed for these subjects, but their reason for ineligibility will be recorded on the Screening Log. Screen failures after the screening visit are not counted towards total study enrollment.

4.7.3 VISIT 2: DAY 0 (INDEX PROCEDURE)

During the index EP procedure, institutional standard of care is to be utilized to treat the subject.

When the subject is connected to the standard EP recording system, during manipulation of catheters or diagnostic tests, intracardiac signals will be recorded using the investigational device in parallel.

The total procedure time is not expected to differ by adding the CathVision ECGenius® system to the EP system as data analysis will occur post procedure. Procedure data will be collected in the Index Procedure Case Report Form (CRF); Adverse Events and Device Deficiencies will be reported through their corresponding CRFs.

4.7.4 VISIT 3: DISCHARGE (NO SPECIFIED WINDOW)

Prior to discharge, the following will be documented:

- Adverse events
- CathVision ECGenius® device deficiencies
- Protocol deviations, if any

Subjects will be considered to have completed all study assessments and will exit the study after this visit.

4.8 STUDY COMPLETION

4.8.1 COMPLETED SUBJECTS

Subjects will be considered complete when all assessments through the Discharge have been performed in accordance with the protocol. There will be no additional clinical follow up requirements for this study.

4.8.2 DISCONTINUED SUBJECTS

Subjects may withdraw consent at any time throughout the course of the study. The investigator may discontinue a subject from the study at any time if they consider that remaining in the study compromises the subject's health or the subject is not sufficiently cooperative. In either event, reason(s) for discontinuation should be documented appropriately.

Possible reasons for study discontinuation include the following:

- Adverse events (AEs) necessitating discontinuation from the study.
- Subject decision (to be specified if possible).
- Investigator decision (to be specified).
- Other reason (to be specified).

The reasons for any subject discontinuation will be documented on the study completion form of the study CRF. If possible, subjects who withdraw before study completion will complete the reporting of data as best possible, at minimum AE assessment and CathVision ECGenius® System device deficiency, if applicable.

4.8.3 PREMATURE STUDY TERMINATION

The Sponsor, Investigator, Competent Authority (CA) or Ethics Committee (EC) have the right to suspend or terminate the study prematurely for any safety, ethical, or administrative reason at any time.

The study will be suspended or prematurely terminated if, in the opinion of the Sponsor, investigator or reviewing EC or CA, the safety of patients and/or data is uncertain. The sponsor should make

sure that the suspension or premature termination will be communicated to the PI and reviewing EC and CA.

CathVision reserves the right to suspend/terminate the investigational site from the study for any of the following reasons:

- Failure to obtain written Informed Consent
- Investigator failure to comply with training or Instructions for Use
- Failure to report SAEs/SADEs/UADEs to Sponsor within 24 hours of knowledge
- Loss of (or unaccounted for) investigational product inventory
- Repeated protocol violations
- Repeated failure to complete case report forms prior to scheduled monitoring visits

In the event of termination of investigator participation, all study-related devices and equipment, as applicable, will be returned to Sponsor.

The decision to resume study enrollment and treatment at the site will be made by the Sponsor. Additionally, the triggering of the stopping/re-activation will promptly be submitted to the involved reviewing EC for approval.

In case of study termination, patients enrolled in the study would be treated and monitored per standard of care and best clinical practices at the investigator's discretion.

4.9 INVESTIGATIONAL DEVICE ACCOUNTABILITY

Documentation of receipt, use, and return of the CathVision ECGenius® System and its parts must be maintained by the Principal Investigator (PI) or his/her designee in a device accountability log. Investigational devices are to be used only in accordance with this protocol and under supervision of the PI or a duly designated person. It is the PI's responsibility to ensure that all study devices are kept in a secure location, with access limited to individuals authorized by the investigator. A record of all study devices (by their lot or serial numbers) received, used, and returned must be maintained by the site until the conclusion of the study. Following accountability of the study devices by the Sponsor or its designee, all study devices will be returned to the Sponsor/Designee as directed in writing by the Sponsor or designee.

5. EXAMINATIONS AND EVALUATIONS

5.1 DEMOGRAPHICS

Subject demographical data, such as date of birth, gender, , height, and weight will be recorded.

5.2 CARDIAC HISTORY

Relevant cardiac history including duration and frequency of arrhythmia(s), their subsequent treatments (e.g., medications, previous ablation) and associated symptoms will be obtained at Screening. All positive and negative findings will be carefully documented. Any new finding discovered during the Screening evaluation and prior to the index ablation procedure will be considered to be part of the cardiac history and will not be recorded as an AE.

5.3 CARDIAC MEDICATIONS

Cardiac anti-arrhythmia medications will be recorded at screening visit, and medications prescribed during the index procedure visit. For each medication, the following information will be collected:

- Medication trade or generic name
- Indication for which the medication was given
- Dose/strength, route, and frequency of administration
- Date started
- Date stopped (or continuation at study completion)

5.4 12 LEAD EKG

A 12-lead electrocardiogram (EKG) will be conducted. The EKG recording will be printed out and will be placed with subject records. A copy of the EKG recording, and report summary will be made available for the study and filed with the subject study records. Any clinically significant abnormalities will be documented.

6. REPORTING OF ADVERSE EVENTS AND DEVICE DEFICIENCIES

6.1 ADVERSE EVENTS DEFINITIONS

An **adverse event (AE)** is any untoward medical occurrence, unintended disease or injury, or the deterioration of a pre-existing medical condition following or during exposure to an investigational medical device, whether or not considered causally related to the investigational medical device.

An untoward medical condition can be symptoms (e.g., nausea, chest pain), signs (e.g., tachycardia, enlarged liver), or clinically significant abnormal results of an investigation (e.g., laboratory findings, electrocardiogram).

A **serious adverse event (SAE)** is any AE which led to any of the following:

- Death,
- Serious deterioration in the subject's health as defined by one or more of the following:
 - a life-threatening illness or injury, or
 - a permanent impairment of a body structure or a body function including chronic diseases, or
 - In-patient or prolonged hospitalization, or
 - medical or surgical intervention to prevent life-threatening illness or injury, or permanent impairment to a body structure or a body function.
- life-threatening fetal distress, fetal death, a congenital abnormality, or birth defect including physical or mental impairment

Additionally, important medical events that may not result in death, be life-threatening or require hospitalization may be considered SAEs when they jeopardize the subject or require medical or surgical intervention to prevent one of the serious outcomes listed above.

Planned hospitalization for a pre-existing condition, or a procedure required by this CIP, without serious deterioration in health, is not considered a SAE.

Adverse device effect (ADE) is an AE related to the use of an investigational medical device. Note, this definition includes AEs resulting from insufficient or inadequate instructions for use, operation, or any malfunction of the investigational medical device. In addition, this definition includes any event resulting from use error or intentional misuse of the investigational medical device.

Serious adverse device effect (SADE) is an ADE that has resulted in any of the consequences characteristic of an SAE.

An **unanticipated adverse device effect (UADE)** is defined as any serious adverse effect on health, safety, any life-threatening problem, death caused by or associated with, a device, if that effect, problem, or death was not previously identified in nature, severity, or degree of incidence in predicate devices, or any other unanticipated serious problem associated with a device that relates to the rights, safety, or welfare of subjects.

6.2 ASSESSMENT OF ADVERSE EVENTS

The need to identify and report AEs is not dependent upon whether or not the clinical event is associated with the use of the study device or procedure. All AEs, regardless of severity, occurring at the index ablation through study completion visit must be recorded in the corresponding CRF. Events occurring prior to the EP procedure must be listed in the cardiac history.

Any Adverse Event(s) that may occur in this study should be reported directly to the Sponsor within 5 working days and to the EC, as required per EC guidelines. Participants experiencing Adverse Events must be treated by the treating physician per standard clinical practice at the institution.

The following information should be obtained for each AE:

- 1. Event description.** Every effort must be made to report the underlying condition or unifying diagnosis for the event. To avoid vague, ambiguous or colloquial expressions, the AE should be recorded in standard medical terminology rather than the subject's own words when possible. Signs and symptoms that are considered unrelated to an encountered syndrome or disease should be recorded as individual AEs on the CRF (e.g., if congestive heart failure and severe headache are observed at the same time, each event should be recorded as an individual AE).

In addition, AEs occurring secondary to other events (e.g., sequelae) should be identified by the primary cause (i.e., a "primary" AE, if clearly identifiable, generally represents the most accurate clinical term to record on AE CRF; events occurring secondary to the primary event should be described in the narrative description of the case.

- 2. Duration:** The date of onset and date of resolution should be reported. Every effort should be made to capture the exact dates.
- 3. Outcome:** The final status of the event should be reported as resolved, ongoing, or if it resulted in death. If the event is present at the final study visit, the ongoing box must be marked.
- 4. Severity:** The severity of the event must be reported as mild, moderate, or severe using the following definitions:

- **Mild:** Aware of sign or symptom, but easily tolerated
- **Moderate:** Discomfort enough to cause interference with usual activity
- **Severe:** Incapacitating with inability to work or do usual activity

5. **Action taken:** Treatment of the event may be reported as none, medical and/or surgical.

6. **Seriousness:** Determined by using the criteria in Section 6.1.

7. **Relationship to device (study device or ancillary device) and/or procedure.** The relationship to device and study procedure will be assessed using the following criteria.

- **Not related:** no temporal association or the cause of the event has been identified, or the device or procedure cannot be implicated.
- **Possible:** temporal association, but other etiologies are likely to be the cause; however, the involvement of the device or procedure cannot be excluded.
- **Probable:** the relationship with the use of the investigational device seems relevant and/or the event cannot reasonably be explained by another cause, but additional information may be obtained.
- **Causal:** temporal association; other etiologies are possible but unlikely.

If any AE is considered to be “possibly related” or “related” to the use of the study device, that event will be classified as an ADE or a SADE. Any reported AEs will be assessed by the reporting investigator.

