6.4 ADVERSE EVENTS REPORTING

The Investigator must complete and submit the AE Case Report Form (CRF) containing all information required by local and/or regional regulations to the Sponsor and Clinical Research Organization (CRO) by fax or email immediately (within 24 hours of awareness).

Sponsor Contact: [name]
[contact]
Email: [contact]

The AE CRF must be signed by a medically qualified investigator (as identified on the delegation of authority log). The signature confirms the accuracy and completeness of the SAE/SADE data as well as the investigator causality assessment including the explanation for the causality assessment.

In addition, the Investigator will report adverse events to the reviewing EC (as applicable) according to the local reporting requirements. Upon notification of SAEs, the Sponsor will initiate and complete a review and evaluation of the event within timeframes that will maintain reporting

compliance with applicable regulatory agencies. The Sponsor or designee will report all SAEs and device deficiencies that could have led to an SADE to the Competent Authority in accordance with EU Regulation 2017/745 and all applicable national regulations.

Investigators must submit safety reports as required by their EC within the required timelines. Documentation of the submission and receipt by the EC of should be retained by the study site.

In the event of a subject's death, the Investigator will make reasonable effort to obtain a copy of the autopsy report and/or death summary. The Investigator will determine the cause of death and its relationship to the investigational device; the Investigator will record results on the AE CRF. The Investigator will include copies of an autopsy report, if available, and/or a death summary with this form.

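### Section 6.2 puts serious adverse events on a 5-working-day sponsor clock, while 6.4 and 4.8.3 require 24 hours; 8.6 adds a third clock for the same form

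*Combined protocol and SAP*

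**What the plan says.** Section 6.2 sets a general rule: "Any Adverse Event(s) that may occur in this study should be reported directly to the Sponsor within 5 working days". It does not say whether the period runs from onset, awareness or something else. The same section has every adverse event recorded on a CRF whatever its severity, and its list of items to collect includes seriousness, "Determined by using the criteria in Section 6.1". Under 6.1, a serious adverse event "is any AE which led to any of the following", followed by the list of serious outcomes.

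Section 6.4 sets a second rule. It begins "The Investigator must complete and submit the AE Case Report Form (CRF" and sends the form to the sponsor and the CRO "by fax or email immediately (within 24 hours of awareness". That sentence is not limited to serious events. Two later sentences in 6.4 do speak of serious events: "The signature confirms the accuracy and completeness of the SAE/SADE data", and "Upon notification of SAEs, the Sponsor will initiate and complete a review and evaluation of the event".

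Section 4.8.3 lists grounds on which the sponsor may suspend or terminate the site. One is "Failure to report SAEs/SADEs/UADEs to Sponsor within 24 hours of knowledge".

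Section 8.6 requires CRFs to be completed three to five working days after the subject's visit and makes no exception for the AE form. Section 10.1 asks the investigator to inform the sponsor of adverse events in good time, without a figure.

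**The concern.** The same investigator reports the same event to the same sponsor, and the protocol gives two time limits that are far apart. Nothing says which limit applies to which class of event. A coordinator who opens 6.2 finds a clear allowance of 5 working days for any adverse event, and nothing there points to the shorter limit in 6.4.

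For a serious event, a site that follows 6.2 to its limit breaks another section of the protocol and gives the sponsor a listed reason to act against it. The sponsor's evaluation starts on notification, and its report of serious events to the Competent Authority, also described in 6.4, cannot come before that notice. Both are put back by however long the site waits.

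**Working it through.** There is no statistical quantity to reproduce, so the check is a side-by-side reading.

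| Section | Events covered as written | Limit | Clock starts | Force |
|---|---|---|---|---|
| 6.2 | any adverse event | 5 working days | not stated | should |
| 6.4 | those on the AE form; no restriction in the submission sentence | 24 hours | awareness | must |
| 4.8.3 | SAEs, SADEs, UADEs | 24 hours | knowledge | discretionary ground for sanction |
| 8.6 | CRFs in general | three to five working days | subject visit | must |
| 10.1 | all adverse events and device effects | no figure | not stated | investigator duty |

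**Step 1: does 6.2 cover serious events?** Yes. By 6.1 every serious event is an adverse event, 6.2 speaks of any adverse event, and 6.2 itself has the investigator classify seriousness. No exception is written.

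**Step 2: does 6.4 cover serious events?** Yes, on either reading. Whether its first sentence means all adverse events or only serious ones, serious events are inside it. For them the 5 working days of 6.2 meet the 24 hours of 6.4, and the 24 hours of 4.8.3 as well.

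**Step 3: does 6.4 cover non-serious events?** Literally, yes. The submission sentence names the AE form without restriction, and 6.2 puts all adverse events on a CRF. But the signature sentence in 6.4 refers to serious-event data, and the review sentence starts from notice of serious events. These suggest that 6.4 may have been written with serious events in mind. No section says so.

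**Step 4: follow a report through the clauses**, assuming that the 6.2 clock also starts at awareness.

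| Report sent | 6.2 | 6.4 | 4.8.3 |
|---|---|---|---|
| within 24 hours, any event | met | met | no ground |
| after 24 hours, within 5 working days, serious | met | breached | ground met |
| after 24 hours, within 5 working days, non-serious | met | breached on the literal text | does not apply |

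**Step 5: does another section settle it?** No. Section 10.1 has no figure. Section 8.6 makes matters less clear: 6.4 wants the AE form both completed and submitted within 24 hours of awareness, whereas 8.6 allows three to five working days to complete a CRF and counts from a different event, the visit.

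**Size.** 24 hours against 5 working days. Turning the latter into hours would need a starting point, a rule for counting the first day and weekends, and a rule on whether the deadline falls at the end of the last day. The protocol gives none of these, so no hour range is stated.

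**The case against.** The best defence is that 6.2 is the general clock and 6.4 with 4.8.3 the expedited clock for serious events. The serious-event wording later in 6.4 and the limited scope of 4.8.3 make this a plausible intention. It stands as a reason not to press the conflict equally for non-serious events. It does not remove the conflict for serious ones, because 6.2 still includes them.

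A second defence is that the clauses can be met together. This is correct: if the 6.2 clock also starts at awareness, a report within 24 hours satisfies 6.2, 6.4 and 4.8.3. A reader might infer that the site faces two duties that cannot both be kept; the text does not support that. The fault is that 6.2 gives a written allowance whose use breaks another section.

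Third, the consequences are bounded. The 4.8.3 sanction is an option for the sponsor, so a reader who infers automatic removal of the site goes too far. A reader might also infer that the safety endpoint would lose events. The documents do not support this either: 6.2 requires every adverse event from the index procedure to study completion to be recorded, and a late report is still a report. The study is one site with 15 to 30 subjects and a passively recording device. Site initiation training (8.5) covers reporting requirements, which may help practice but does not correct the text.

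**Conclusion.** The contradiction holds for serious adverse events on any reading of 6.4: 5 working days in 6.2 against 24 hours in 6.4 and 4.8.3. For non-serious events it holds only on the literal wording of 6.4, and the likelier explanation is a serious/non-serious split that was meant and never written. Section 8.6 is a third clock on the same form, also without an exception.

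The trace of reports through the clauses assumes that the 6.2 period starts at awareness, which 6.2 does not say. The documents do not give the frequency of late reports, and none is claimed.

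A reader might add section 6.6, which runs its 24-hour clock for device deficiencies from occurrence rather than awareness. That is a separate minor wording point: it concerns another form and another kind of report, and contradicts neither 6.2 nor 6.4.

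**What to change.** Reconcile 6.2, 6.4, 4.8.3 and 8.6 so that serious and non-serious adverse events each have one stated sponsor-reporting clock with a stated start. In particular:

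- **6.2** should no longer cover serious events with a clock that contradicts 6.4 and 4.8.3, and should say what starts any period that it keeps.
- **6.4** should say outright whether its submission sentence applies to all adverse events or to serious ones only.
- **4.8.3** should refer to the same event classes and the same starting point as the reporting sections.
- **8.6** should except the AE form or defer to the adverse-event clock.

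The length of each limit is for the sponsor to settle against the applicable requirements; this point does not choose it. The cost is a wording amendment to four sections, with Ethics Committee approval as 8.8 requires. No visit, data item or patient contact is added.
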